**Table 1.**

Stratum specific sample size*	Baseline uptake of health facility HIV testing	Intervention component distribution	Power for relative increase in HIV testing uptake among those with the intervention component vs. those without		
			RR=1.75	RR=2.0	RR=2.25
135	20%	40%	0.484	0.702	0.856
		50%	0.458	0.724	0.868
		60%	0.432	0.622	0.824
		70%	0.346	0.576	0.762
135	25%	40%	0.628	0.852	0.954
		50%	0.596	0.832	0.952
		60%	0.604	0.814	0.964
		70%	0.501	0.708	0.874

135	30%	40%	0.772	0.924	0.994
		50%	0.738	0.928	0.996
		60%	0.726	0.924	0.998
		70%	0.592	0.850	0.976
135	35%	40%	0.868	0.990	1.000
		50%	0.832	0.974	1.000
		60%	0.830	0.980	1.000
		70%	0.744	0.952	0.996
135	40%	40%	0.922	1.000	1.000
		50%	0.924	1.000	1.000
		60%	0.932	1.000	1.000
		70%	0.852	0.990	1.000

\*N=135 assumes ~10% test HIV+ and are excluded and the remaining participants are divided equally into two strata of a modifier (e.g., 50% female)

**Table 2.**

Stratum specific sample size*	Baseline uptake of health facility HIV testing	Intervention component distribution	Power for relative increase in HIV testing uptake among those with the intervention component vs. those without		
			RR=1.75	RR=2.0	RR=2.25
115	20%	40%	0.464	0.660	0.814
		50%	0.412	0.596	0.802
		60%	0.346	0.536	0.770
		70%	0.298	0.468	0.654
115	25%	40%	0.574	0.780	0.928
		50%	0.546	0.782	0.932
		60%	0.536	0.746	0.898
		70%	0.412	0.624	0.820
115	30%	40%	0.646	0.896	0.974
		50%	0.676	0.902	0.986
		60%	0.638	0.852	0.958
		70%	0.516	0.796	0.934
115	35%	40%	0.796	0.972	0.998
		50%	0.802	0.972	0.998
		60%	0.716	0.958	0.998
		70%	0.638	0.910	0.994
115	40%	40%	0.908	0.992	1.000
		50%	0.914	0.996	1.000
		60%	0.858	0.990	1.000
		70%	0.794	0.986	1.000

\*N=115 assumes ~5% test HIV+ and are excluded and the remaining participants are divided unequally into two strata of a modifier (e.g., 40% female or other modifier)

## 5. Methods

## Measurement of Results

*Community member (those offered HIV testing) and healer outcomes:* Participants will complete both a baseline and 7-month post-enrollment questionnaire using the ACASI-system on a tablet. Data collection at 7 months will include the baseline survey and additional questions about uptake of HIV testing outside of the study and feedback about the acceptability and satisfaction with the study experience. These will be conducted by a study assistant based in the Agincourt area who is fluent in English and xi-Tsonga. The number of participants approached, the number who agree to testing and counseling (including testing outcome), and reports on the impact of performing HIV testing and counseling on healer income will be collected by the traditional healer. Health clinic research staff will collect uptake of testing during one of the “Open House” events and during non-open house days (if, for example a patient seeks testing during regular clinic hours). Clinical data will be accessed using “Clinic Link” which allows us to gain access to relevant clinical data, including ART uptake and retention in care. Data from clinical providers who participate in the stigma reduction intervention will complete surveys at study initiation and immediately after the study has concluded.

### **Table 3: Outcomes**

#### Traditional Healer Outcomes

**Acceptability Endpoints:** (1) Percent of eligible healers who enroll in the training program and (2) Acceptability of the intervention scale (as used in Aim 2).

**Feasibility Endpoints:** (1) Percent of healers who complete training, (2) Change in self-reported healer income, and (3) Feasibility of the intervention (as used in Aim 2).

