## **2. Objectives**

The objective of this proposal is to conduct a pilot test of a program aimed at training traditional healers to conduct HIV testing and implementing HIV testing among people living in Bushbuckridge, South Africa.

Pilot Healer-initiated HIV testing uptake and linkage to prevention services. Trust in allopathic health care and HIV stigma will be measured among participants at study enrollment and at month seven.

*Hypothesis:* HICT will increase trust in allopathic health care and reduce HIV stigma.

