### Inclusion Criteria

1. Traditional healers  $\geq$  18 years of age, who are registered as traditional healers with the government of South Africa, are currently practicing in the Bushbuckridge area, and are trained to provide HIV testing.
2. Biomedical practitioners  $\geq$  18 years of age, who are currently providing HIV-related health care services to patients at government or private health facilities in Bushbuckridge.
3. Community members  $\geq$  18 years of age, who have not received an HIV test result in the past year and who currently live in Bushbuckridge.

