### Exclusion Criteria

1. Traditional healers who do not pass their HIV counseling and testing certification.
2. Biomedical practitioners who do not interact with patients seeking treatment for HIV.
3. Community members who are not out sound mind or body during the recruitment (inebriated, too sick to leave the house) and community members with a previous positive HIV test result.

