## Training Activities

To enable traditional healers to acquire the skills necessary to undertake home-based HIV testing as well as HIV coping skills counseling, traditional healers selected to participate will enroll in a 2-week course used with HIV counselors that includes certification to conduct HIV counselling and testing and basic lay counseling to develop patient coping strategies. During the testing and counseling course, 9 topics will be covered including: 1) epidemiology and pathophysiology of HIV/AIDS and disease stages, 2) attitudes and social views of HIV, an introduction to HIV counselling and testing, legal and ethical issues of HIV and HIV testing, 3) pre- and post- test counselling, 4) performing an HIV rapid test and interpretation of the results, 5) psychological stress as a result of a positive test, 6) identifying depressive symptoms (and how to refer a patient to psychological services), 7) referral and management of HIV, 8) counseling patients on primary and secondary prevention methods (including condom use, Pre-Exposure Prophylaxis [PrEP]) after HIV testing) and 9) safe disposal of HIV testing equipment. Counseling support will include the development of coping strategies to overcome the negative effects of HIV stigma, risk reduction, and linkage with appropriate community organizations.

The course content will be delivered in an iterative fashion and trainees will have ample opportunity to ask questions with facilitated discussions. Traditional healers/trainees will be asked to orally respond to questions posed by the trainer throughout the training to gauge comprehension as new concepts are introduced. More formally, both a written and practical assessment will be administered. The trainee will be required to pass to be considered proficient to undertake HIV counselling and testing. Fidelity to the intervention, including the safety of the intervention for those tested by the healers, will be monitored via monthly observation using a checklist of procedural activities. This same mechanism is currently employed with community health workers who are providing home-based HIV counseling and testing, to which we have not experienced any difficulty implementing.

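### The healer eligibility criteria contradict the enrolment-in-training endpoint, and the completion-of-training endpoint has no stated denominator

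*Combined protocol and SAP*

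**What the plan says.** Section 4 has one inclusion criterion for healers. They must be at least 18, government-registered, and must be healers who "are currently practicing in the Bushbuckridge area, and are trained to provide HIV testing". The matching exclusion criterion reads "Traditional healers who do not pass their HIV counseling and testing certification".

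Table 3 in section 5 lists, under healer acceptability, the "Percent of eligible healers who enroll in the training program" and, under healer feasibility, the "Percent of healers who complete training". Each group also includes a scale, and the feasibility group includes change in self-reported income.

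Training Activities describes the course as something that follows selection: "traditional healers selected to participate will enroll in a 2-week course used with HIV counselors". The course ends in a written and a practical assessment: "The trainee will be required to pass to be considered proficient to undertake HIV counselling and testing". Section 2 makes training part of what is piloted, since the aim is to "conduct a pilot test of a program aimed at training traditional healers to conduct HIV testing".

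**The concern.** An endpoint that measures how many eligible healers enter training needs a denominator fixed before training. The stated denominator is fixed after it. Healers who decline the course are not trained, so they are not eligible. Those who drop out are not trained either, and those who fail are excluded by name. The people whose absence the percentage should reveal are removed before it is calculated.

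At stake is how willing healers are to take the course and, depending on the denominator used, how many finish it. Someone planning a larger programme would want to know how many healers must be invited to obtain one certified tester. A reported 100% would say nothing about that.

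**Working it through.** The documents state no number of healers, no expected enrolment or completion rate and no feasibility threshold. There is no figure to reproduce, so the check concerns numerators and denominators.

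**Definitions.** Let A = healers invited to the course, E = enrolled (taken here as starting it), C = completed it, P = passed certification, with A ≥ E ≥ C ≥ P.

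**Eligible set under section 4, if the training meant is the study course.**
- Inclusion (trained) leaves at most C.
- Exclusion (certification not passed) reduces this to P.

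**Enrolment endpoint.** Everyone in the eligible set has enrolled, so the percentage is P/P = 100%, whatever A, E and C are. If only the inclusion criterion is applied, it is C/C = 100%. The informative quantity is E/A.

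**Enrolment endpoint, if training before the study is meant.** The denominator is healers who can already test. The share of them who take a course to learn testing has no clear meaning as acceptability of the programme.

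**Completion endpoint.** Table 3 says healers, not eligible healers, so two readings are open.
- Course starters as denominator: C/E, which is informative.
- Section 4 eligibility applied: P/P = 100%.

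Table 3 does not choose between them. It also does not say whether completing includes passing, although Training Activities treats the course and the assessment as distinct. C/E and P/E are different quantities.

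**Illustration.** All rates are assumed, because the documents give none. The rates are for enrolment among those invited, completion among starters, and passing among completers.

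| Assumed rates | Enrolled/invited | Completed/started | Certified/started | Certified/invited | Enrolment, literal criteria |
|---|---|---|---|---|---|
| 90%, 95%, 95% | 90% | 95% | 0.95 × 0.95 = 90% | 0.90 × 0.9025 = 81% | 100% |
| 70%, 80%, 90% | 70% | 80% | 0.80 × 0.90 = 72% | 0.70 × 0.72 = 50% | 100% |
| 50%, 60%, 80% | 50% | 60% | 0.60 × 0.80 = 48% | 0.50 × 0.48 = 24% | 100% |

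The last column does not depend on the number invited. Completion is also 100% in every row if the eligibility criteria are applied to it.

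**Precision.** If 20 healers started and 14 certified (again assumed), certified/started is 14/20 = 70%, with an exact (Clopper-Pearson) 95% interval of 46% to 88%. This is a certification rate. Completion in the same example could lie anywhere from 70% to 100%, depending on how many of the other 6 finished the course and failed.

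**Does another section repair it?** Measurement of Results lists counts of participants approached and agreeing to testing, but no counts of healers invited, starting, completing or failing. Data Management mentions observations of training without defining such counts. The Data Analysis section does not cover healer endpoints.

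**The case against.** The best defence is that the staged design is already visible. The certification exclusion can operate only after a healer has attempted certification, training follows selection, and patients are recruited through healers who are already trained. On this reading section 4 describes healers who deliver testing, and a study team would be unlikely to report a circular percentage.

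Much of this stands as a guess at intent, and for completion it matters: starters are the natural denominator there. A reader might infer that both training endpoints must come out at 100%. The text does not support that for completion, which is ambiguous. The defence does not rescue enrolment, because that endpoint names eligible healers and the protocol gives no other definition of healer eligibility.

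It is also fair to say that the reach is limited. The Limitations section names uptake of healer-initiated testing, stigma and mistrust, and linkage as the elements needed for a larger trial. Healer enrolment and completion are not among them.

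**Conclusion.** The concern holds as a contradiction between stated rules. Under the criteria as written, the enrolment endpoint is 100% by construction or meaningless. The completion endpoint lacks a denominator, and is 100% only if eligibility is applied to it. The 100% result assumes that the training in the inclusion criterion is the study course and that its denominator is exactly the section 4 eligible set. How far it would lie from the true rate cannot be known from the documents; the assumed rates above give gaps of 10 to 50 percentage points for enrolment.

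A reader might go further and conclude that the pilot cannot show feasibility. The documents do not support that. Enrolment is listed under acceptability. The two scales, income change and uptake of healer-based testing are not fixed by these criteria, and neither are the patient primary endpoints or the power tables, which concern community members. This should be corrected, but it does not undermine the main patient analysis.

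**What to change.** Split the healer criteria in section 4 by stage.
- *Training stage:* registered, practising in the area, at least 18 years old.
- *Testing-delivery stage:* the above, plus the protocol's existing training and certification conditions.

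In Table 3, report three separate proportions with exact confidence intervals:
1. enrolled / training-stage-eligible healers invited;
2. completed the course / started;
3. certified / started.

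State what completing the course means, apart from passing the assessment. Keep a log of every healer invited, started, completed and certified. Retain non-certified healers in these three counts, but not in outcomes that depend on performing testing: Measurement of Results ties the income report to that activity.

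The cost is protocol wording and a simple log, with no extra participants. The reported percentages may be less favourable, and with few healers the intervals will be wide.

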#### Patient Outcomes

**Primary Continuum of Care Endpoints:** (1) Uptake of health facility HIV-test at 6-months (if previously negative or refused test), (2) Uptake of ART services, if positive.

**Secondary Endpoints:** (1) Mistrust towards the allopathic health system, (2) Change in levels of HIV-related stigma among those who test negative, (3) Change in levels of conspiracy beliefs

**Feasibility Outcome:** (1) Uptake of healer-based HIV testing

## *Clinician outcomes:*

We will assess baseline, midterm (after the first training) and end line (after the second training) stigma levels among providers using a Likert-style scale that will assess attitudes towards PLHIV, traditional healers (and healers providing HIV testing in the community), people who use traditional healers, sex workers, men who have sex with men, immigrants, young pregnant women who are not married, and sex workers. We will ask if health care workers: (1) would prefer to not provide services; (2) believe that sub-populations put clinicians at higher risk of acquiring HIV; (3) agree that specific populations engage in immoral behavior; and (4) agree that specific populations deserve their HIV diagnosis.

## Study Procedures

Participants will be recruited among those who present for health care services from one of our traditional healers trained in conducting HIV counseling and testing. Participants will be recruited after their healer consultation is completed to ensure we do not impact their services. Healers will screen potential participants for eligibility (no HIV test in past year, over 18 years of age, live in Agincourt) and if they are eligible, the healers will ask if they are willing to participate in a research study. Healers will state clearly that there is no obligation to participate and that choosing not to participate will in no way impact their health care from this traditional healer. Healers will consent participants via an online consent form via tablet, so all consent forms will be online and backed up to the secure Vanderbilt REDCap cloud.

## Training Activities

To enable traditional healers to acquire the skills necessary to undertake home-based HIV testing as well as HIV coping skills counseling, traditional healers selected to participate will enroll in a 2-week course used with HIV counselors that includes certification to conduct HIV counselling and testing and basic lay counseling to develop patient coping strategies. During the testing and counseling course, 9 topics will be covered including: 1) epidemiology and pathophysiology of HIV/AIDS and disease stages, 2) attitudes and social views of HIV, an introduction to HIV counselling and testing, legal and ethical issues of HIV and HIV testing, 3) pre- and post- test counselling, 4) performing an HIV rapid test and interpretation of the results, 5) psychological stress as a result of a positive test, 6) identifying depressive symptoms (and how to refer a patient to psychological services), 7) referral and management of HIV, 8) counseling patients on primary and secondary prevention methods (including condom use, Pre-Exposure Prophylaxis [PrEP]) after HIV testing) and 9) safe disposal of HIV testing equipment. Counseling support will include the development of coping strategies to overcome the negative effects of HIV stigma, risk reduction, and linkage with appropriate community organizations.

The course content will be delivered in an iterative fashion and trainees will have ample opportunity to ask questions with facilitated discussions. Traditional healers/trainees will be asked to orally respond to questions posed by the trainer throughout the training to gauge comprehension as new concepts are introduced. More formally, both a written and practical assessment will be administered. The trainee will be required to pass to be considered proficient to undertake HIV counselling and testing. Fidelity to the intervention, including the safety of the intervention for those tested by the healers, will be monitored via monthly observation using a checklist of procedural activities. This same mechanism is currently employed with community health workers who are providing home-based HIV counseling and testing, to which we have not experienced any difficulty implementing.

Health care providers will receive training in stigma reduction and structural changes to engage these previously stigmatized populations. We will focus on four essential elements identified by Nybalde (1) Participatory learning via the provision of information about the impact of stigma on health care outcomes and; (2) Skill building activities (communication, openness) with health care providers to develop skills to work with stigmatized populations (3) Contact with the stigmatized group, including healers and their patients via testimonials and (4) group activities to develop empathy, humanize this stigmatized group, and break down stereotypes.

The stigma reduction training will be conducted by clinician-trainers based at the University of the Witwatersrand. The first part of the training will include an initial two-day training followed by a one-day training two months later that include the following components:

Title of exercise/session	Educational technique	Intended learning outcomes
1. Naming stigma through pictures	In this session, prepared pictures based on personal stories of stigma are viewed. Then, the participants discuss and analyze the forms, causes, and effects of stigma.	Participants discuss what similar stigma takes place in different contexts and start to share stories of what they have personally witnessed.
2. Our own experiences of stigma	This exercise asks participants to think about a time in their life when they felt stigmatized, share this with a partner, and discuss with the larger group	Gives participants a better understanding of the personal feeling and the long-term impacts of stigmatization
3. Key populations stigma problem tree	Using colored cards and markers, participants discuss and write forms of stigma faced by key populations at risk of HIV. The cards are posted on a wall with the causes of stigma representing "roots"	Helps participants to recognize the causes of stigma and how the resulting effects are manifested.

	of a tree at the bottom, actual forms of stigma as the “trunk” of the tree in the middle, and effects of stigma as the tree’s leaves and branches.	
4. Value clarification	Participants fill and individual questionnaire about their personal values and reflect and discuss how these values affect their judgement of others.	Recognition of how personal attitudes and beliefs influence stigmatizing behavior.
5. Things people say	Group brainstorming of what people say about different key populations at risk of HIV.	Understanding how language is used to stigmatize different population subgroups and how words may have harmful impacts.
6. Traditional healers and HIV	Small group discussions about different case studies based on health service experiences of traditional healers, and those who seek services from traditional healers.	Enhanced ability to identify stigma-related barriers for people who use traditional medicine and traditional healers to access and receive appropriate health services.
7. Be the change	Paired role playing to practice challenging stigma in the workplace and elsewhere.	Increased ability to personally challenge or change stigmatizing attitudes among peers and in other situations
8. Writing a charter for stigma-free service	Small group work discussing ideas to promote stigma-free health services. Ideas are promoted in a larger group, and ways forward are discussed.	Understanding of how to develop ideals for promoting stigma-free services when service providers return to their workplace.

Table 5: Stigma Training for providers

**Data Collection:** Participants will complete both a baseline and 7-month post-enrollment questionnaire using the ACASI-system on a tablet. Data collection at 7 months will include the baseline survey and additional questions about uptake of HIV testing outside of the study and feedback about the acceptability and satisfaction with the study experience. These will be conducted by a study assistant based in the Agincourt area who is fluent in English and xi-Tsonga. The number of participants approached, the number who agree to testing and counseling (including testing outcome), and reports on the impact of performing HIV testing and counseling on healer income will be collected by the traditional healer. Health clinic research staff will collect uptake of testing during one of the “Open House” events and during non-open house days (if, for example a patient seeks testing during regular clinic hours). Clinical data will be accessed using “Clinic Link” which allows us to gain access to relevant clinical data, including ART uptake and retention in care. Data from clinical providers who participate in the stigma reduction intervention will complete surveys at study initiation and immediately after the study has concluded.

Time point	Activity	Data Collection
Baseline	Enrollment	Demographics, HIV Stigma, Trust in allopathic provider, belief in HIV test, use of traditional medicine, perceived risk of HIV
Baseline	Healer-initiated C&T, including stigma reduction	Attendance, HIV status, enrollment in care and treatment if positive
Month 6	HIV re-test	Attendance, HIV status, enrollment in care and treatment if positive
Month 7	Follow-up survey & qualitative questions	HIV Stigma, Trust in allopathic provider, belief in HIV test, use of traditional medicine, perceived risk of HIV, experience with the healer-clinician collaborative

Table 6: Project Activities and Data Collection Points

